### **Introduction**

Hyperlipidemia as exemplified by familial hypercholesterolemia is associated with increased platelet activation and an underlying pro-coagulant state. Hyperlipidemia primes platelets and increases platelet activation in response to various agonists. Plasma cholesterol levels appear to have a critical role in modulating platelet activity as hypercholesterolemia increases platelet activation more potently than hypertriglyceridemia. Plasma levels of platelet activation markers such as thrombin-antithrombin complex (TAT), soluble P-selectin (sP-selectin), soluble CD40L (sCD40L) or P-selectin exposure at surface of platelets are increased in hypercholesterolemic patients. Increased levels of the platelet activation markers are associated with increased platelet membrane cholesterol content in hypercholesterolemia. Hyperlipidemia increases platelet activation likely via multiple mechanisms. Oxidized LDL or oxidized phospholipids, which are increased in hyperlipidemia, serve as ligands of platelet CD36 and activate platelets. *In vitro* cholesterol-loading increases while cholesterol-unloading decreases human platelet activation. Recently, we showed that cholesterol enrichment of platelets increased platelet activation via a mechanism involving ↓LYN Kinase activation→↓SHIP-1 activity→↑PIP3→↑AKT activity.

Statins may show antithrombotic properties. The PROVE-IT trial, a study to assess the impact of statins on acute coronary syndrome (ACS), demonstrated an early beneficial effect after 30 days of follow-up that significantly reduced the risk of death, MI or rehospitalization. A retrospective study of 1616 patients (PRISM) also showed significant reduction of the risk during 30 day follow-up in ACS patients with statin therapy. Additional human studies suggest that the benefits may come partly from the antithrombotic properties of statins. Statins reduced the level of TAT, sP-selectin, sCD40L and P-selectin exposure at surface of platelets. Reduced levels of P-selectin at the platelet surface were associated with reduced platelet cholesterol content in subjects treated with statins. These studies suggest an early direct effect of statins on platelets and a late prolonged effect that is associated with progressive reduction of plasma LDL-cholesterol levels. Both the early and late effects are proposed to lower platelet activation and contribute to the reduced risk. Consistent with the idea that cholesterol enrichment increases platelet activation, infusions of a reconstituted HDL (rHDL) preparation

reduced *ex vivo* platelet activation in diabetic subjects, likely by promoting cholesterol efflux from platelets.

Human genome wide association studies have revealed novel genetic loci associated with coronary heart disease. One such locus resides in *LNK/SH2B3* which in mice is expressed in hematopoietic cells and suppresses thrombopoietin signaling via its receptor MPL. Using human cord blood, we recently showed that the common TT risk genotype (R262W) of *LNK* is associated with expansion of hematopoietic stem cells and enhanced megakaryopoiesis, demonstrating reduced LNK function and increased MPL signaling. To model the human reduced LNK function associated with the TT risk genotype, we used *Lnk*-/- mice. In mice, hematopoietic *Lnk* deficiency led to accelerated arterial thrombosis, but only in the setting of hypercholesterolemia. In platelets LNK deficiency increased MPL signaling, while cholesterol loading decreased SHIP-1 activation, acting convergently to increase AKT and platelet activation. Increased platelet activation combines with hypercholesterolemia induced myelopoiesis to promote pro-thrombotic platelet/leukocyte aggregate formation and accelerated atherogenesis. Atherosclerotic lesions were characterized by larger size, increased necrotic cores and increased leukocyte-derived DNA nets.

These findings suggest the possibility that in humans, the common LNK variant rs3184504 impacts platelet activation in a fashion dependent on plasma cholesterol levels. In light of these findings, we propose the following studies as an investigator initiated study. The primary goal is to assess the impact of Evolocumab therapy on platelet function of FH patients in a randomized, double blind study. The secondary goal is to determine if platelet activation or the response to Evolocumab therapy is modified by rs3184504 polymorphism. We believe that these investigations will complement ongoing studies to demonstrate that Evolocumab reduces athero-thrombotic risk and aid the decision-making as to whether Evolocumab can reduce the atherothrombotic risk in ACS patients.

#### **Proposed studies.**

- A. Sample collection: All adult male and female subjects who have a clinical diagnosis of familial hypercholesterolemia (FH) and who are referred to [name] Practice for treatment with PCSK9 inhibitor, with LDL cholesterol levels  $\geq 70$  mg/dl on baseline

treatment with statins and/or ezetimibe or intolerant to statin and/or ezetimibe. The platelet counts in peripheral blood should be  $\geq 100,000$  per microliter. The subjects that meet these criteria will be recruited for the study.

Blood will be collected as shown in Fig. 1 in the morning from the resting and fasting subjects. An aliquot will be collected for genomic DNA and platelet-rich plasma (PRP) preparation.

B. Power Calculation:

The effect of PCSK9

inhibitors, including evolocumab, on platelet activation measures has not been assessed previously. However, our hypothesis is based on the LDL-cholesterol lowering effect of evolocumab, and evolocumab has been demonstrated to have at least as potent an effect on LDL lowering as statins. Statin therapy in hypercholesterolemia patients results in 50% reduction in LDL-cholesterol levels and add-on evolocumab therapy indicated an additional 50-60% reduction. Therefore, we base our power estimates on platelet activation data available for statins.

Primary measure/platelet aggregation - The primary measurement will be ADP-stimulated platelet aggregation as assessed by the commercially-available VerifyNow P2Y12 assay (Accriva Diagnostics). The assay read-outs are 1) PRU, platelet reactivity units (specific for P2Y12 receptors); 2) BASE, total platelet function despite P2Y12 receptor blockage; and 3) IPA, percent platelet P2Y12 inhibition calculated as  $[(\text{BASE} - \text{PRU}) / \text{BASE}] \times 100$ . Two reports involving patients on antiplatelet therapy with high residual platelet reactivity demonstrated an effect of statins on lowering platelet aggregation via the VerifyNow assay. In CAD patients treated with clopidogrel, the addition of atorvastatin for 30 days resulted in an absolute mean difference of  $102 \pm 54$  PRU compared to baseline, corresponding to a  $37 \pm 14\%$  IPA. In a separate study of CAD/diabetic patients treated with clopidogrel, the addition of atorvastatin for 30 days resulted in an absolute mean difference of  $106 \pm 75$  PRU compared to baseline, corresponding to a  $33 \pm 20\%$  IPA. Similar effect sizes and variabilities of statins on reductions in platelet aggregation were observed in type II

Step	Procedure
1	Venipuncture with G21 butterfly needle.
2	Collect 2 ml blood into sodium citrate tube as waste tube
3	Collect 3x2 mL blood into 3 Greiner Vacuette tubes containing 3.2% sodium citrate. For VerifyNow assays.
4	Collect 2x3 ml blood into 2 Greiner Vacuette tubes containing 3.2% sodium citrate. For platelet activation assays.
5	Collect 1x2 ml blood into Vacuette tube containing EDTA. For CBC assay.
6	Collect 2x2 ml blood for metabolic panel, lipid panel and TSH assays.
7	Collect urine for urinalysis.
8	Pregnancy test with stick assay.

hyperlipidemic patients using light transmittance aggregometry. The relative reductions were reported as  $30 \pm 23\%$  (pravastatin),  $19 \pm 16\%$  (atorvastatin), and  $22 \pm 22\%$  (simvastatin).

[figure not shown]
The reference range for the VerifyNow assay in individuals not on antiplatelet therapy is 180-376 PRU. These data are continuous and normally distributed. Thus, means and standard deviations will be used to describe reductions in platelet aggregation. Based on reported literature indicating additional effects of statins on platelet function following 30-day vs shorter periods of treatment, we have revised our experimental design to have a primary endpoint of 30-day treatment. Within-group thirty day evolocumab treatment will be tested by one-group paired t-test (two-sided) using each subject as its own control (evolocumab treatment vs vehicle pre-treatment control). Between-group thirty day evolocumab treatment will be tested by standard two-group t-test (two-sided, evolocumab vs vehicle control group run in parallel). The sample size estimates have been run using one-group, paired t-test published data. Using PRU mean difference = 102, SD = 54, power = 0.8 and alpha = 0.05, we estimate 6 subjects. Since the effects of statins on platelet aggregation may be mediated by both LDL-lowering and non-LDL-lowering mechanisms, we can calculate the sample size based on 50% reduced mean difference (PRU = 51). Then, we estimate 11 subjects. An equal number of subjects will be required for the placebo group run in parallel. Target enrollment will include all patients screened; we estimate that 10% may not be eligible based on exclusion criteria and/or may not return for scheduled blood draws. Thus, for 80% power, the target enrollment is 24 subjects over two years.

Secondary measures – Secondary measures will include various cellular and circulating markers of platelet activation measured by flow cytometry or commercially-available enzyme-linked immunoassays (ELISAs). The target enrollment of 24 subjects should provide at least 80% power to detect differences between treatment groups based on data reported in the literature. For example, platelet P-selectin level measured by flow cytometry and reported as % positive cells (out of 50,000 cells counted) showed a mean reduction  $\pm$  SD of  $10.9 \pm 6.0$  (simvastatin),  $10.9 \pm 5.6$  (atorvastatin),  $7.2 \pm 6.8$  (fluvastatin) and  $9.0 \pm 6.8$  (pravastatin) following 30 days of statin treatment in hypercholesterolemic patients compared with untreated controls. In a separate study of stroke patients with hypercholesterolemia, platelet P-selectin showed a mean reduction of  $41 \pm 27\%$  positive cells in response to thrombin following 6 months of treatment with simvastatin compared to baseline measurements in the same subjects before statin treatment. An additional

effect of simvastatin treatment was observed for soluble P-selectin serum concentrations measured by ELISA. Soluble P-selectin showed a mean reduction of  $46.4 \pm 49$  ng/ml compared to baseline measurements in the same subjects before statin treatment. Other secondary measures include VerifyNow IIb/IIIa and VerifyNow Aspirin assays.

C. Study Design: Amgen will provide Evolocumab and placebo as open label. An independent biostatistician will generate a randomization table and provide it to Research Pharmacy of CUMC and Research Pharmacy will randomize the subjects accordingly. All patients recruited will start with placebo and blood and urine samples will be collected at day 7 and day 14. Then, the subjects will be randomized so that half will continue to receive placebo and half will receive Evolocumab via subcutaneous injection of 140 mg every 14 days. Blood and urine samples will be collected at day 21 and day 28. Then, all patients will receive Evolocumab 140 mg every 14 days and the treatment will continue.

Blood and urine samples will be collected following Evolocumab therapy at day 84 and 196 (Fig. 2). While every effort will be made to collect the blood and urine samples on the indicated time points, variation for the sample collection within 1-3 days at the indicated time point will be

allowed. The power of this design is that we can compare any changes due to Evolocumab therapy relative to a placebo control.

Based on the power calculations as detailed above, recruitment of total 20 participants into this study will give ~80% power for statistical significance of 0.05. We target to recruit 24 subjects over 2 year period. However, we anticipate that some participants will drop out from the study and incomplete data will be obtained. We will continue to recruit the subjects until the complete data sets for 22 subjects are obtained. Incomplete data from the dropout may not be used unless data up to 28 days at least are collected.

D. Genotyping: rs3184504 genotyping will be performed using the genomic DNA samples

and rs3184504 specific PCR genotyping primers from Invitrogen.

- E. Assays: We propose to use a clinically validated system, VerifyNow, as the assay for assessment of platelet activation state. Compared with other assays, this system requires ~2 ml whole blood, with minimal ex vivo manipulations, minimal hands-on time and no pipetting or sample preparation. It is fast (10 min for result presentation) and approved as a clinical lab test of platelet reactivity. Thus, the results obtained this way should be more reliable when the data need to be compared with results from other studies using the same assay. In principle, this assay is designed to measure platelet function based upon the ability of activated platelets to bind fibrinogen. Fibrinogen-coated microparticles aggregate in whole blood in proportion to the number of unblocked platelet GP IIb/IIIa receptors. Light transmittance increases as activated platelets bind and aggregate fibrinogen-coated beads. The instrument measures this change in optical signal caused by aggregation. We propose to use VerifyNow IIb/IIIa, VerifyNow PRUtest, and VerifyNow Aspirin assays, testing platelet responses to thrombin-like peptide, ADP and arachidonic acid, respectively. In addition to the VerifyNow assay, basal level of P-selectin and active form of GPIIb/IIIa at surface of platelets will be determined by flow cytometry. In order to reduce the variation generated by manipulation of blood samples in vitro, we will use 1% paraformaldehyde to fix an aliquot of the whole blood sample and basal levels of P-selectin and active GPIIb/IIIa at surface of platelets will be determined by flow cytometry after staining with specific P-selectin or PAC-1 antibody (PAC-1 specific for active GPIIb/IIIa). Plasma levels of TAT, sP-selectin and sCD40L will be determined by ELISA assays. Levels of plasma LDL cholesterol, HDL cholesterol, triglyceride and platelet total cholesterol content will be determined. All these assays are validated assays.
- F. Analysis: The primary hypothesis is that Evolocumab will reduce thrombin-peptide stimulated platelet activation as determined by VerifyNow. Secondary hypothesis is related to basal and ADP or arachidonic acid stimulated activation, direct measurements of platelet activation by flow cytometry or levels of the surrogate markers. This will help assess the validity of these markers for larger ongoing studies that we are performing in collaboration with Amgen using EDTA plasma samples obtained in phase 2 development studies of Evolocumab. Even though the statistical power is limited by small sample size, the potential modification of these phenotypes by rs3184504 polymorphism will be examined.

**Time Frame:** two years

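### Patients with and without a statin are mixed in a small trial with no stated stratification and no covariate in the between-group test: a likely loss of precision that is cheap to recover

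*Combined protocol and SAP*

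**What the plan says.** Section A of Proposed studies takes adults with familial hypercholesterolemia and raised LDL cholesterol on "treatment with statins and/or ezetimibe or intolerant to statin and/or ezetimibe". It gives no expected split between patients taking a statin and patients not taking one.

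Section C describes allocation: "An independent biostatistician will generate a randomization table and provide it to Research Pharmacy of CUMC". After a placebo run-in sampled at days 7 and 14, "half will continue to receive placebo and half will receive Evolocumab", with samples at days 21 and 28. No stratification factor or block size is given.

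Section B gives the comparison of arms: "Between-group thirty day evolocumab treatment will be tested by standard two-group t-test (two-sided, evolocumab vs vehicle control group run in parallel"). No covariate is named, and the outcome scale is not stated. On sample size it says: "The sample size estimates have been run using one-group, paired t-test published data". The inputs are a statin effect of 102 PRU with SD 54, halved to 51 PRU for evolocumab, giving 11 per group and a target of 24.

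Section B also reports 106 PRU from a second statin study, and relative reductions of 19-30% in aggregation in type II hyperlipidemic patients by a different assay. On LDL it says: "Statin therapy in hypercholesterolemia patients results in 50% reduction in LDL-cholesterol levels". The Introduction attributes to statins an early direct effect on platelets as well as a later, LDL-linked one.

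**The concern.** The plan treats statins as a strong influence on the measure it is sized on, then leaves statin use free to differ between two arms of about 11 and does not adjust for it. If patients off statins start with higher PRU, two things follow on the raw scale. The mixture widens the spread within each arm and so lowers power. A chance excess of statin-free patients in one arm also moves that trial's observed difference.

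A second route is a different response. By the plan's figures a statin halves LDL and evolocumab removes a further 50-60%. For the same untreated LDL, a statin-free patient would then lose about twice as much LDL in mg/dl. The hypothesis rests on LDL lowering, so the PRU response might differ too. The documents give no PRU change per mg/dl, so this cannot be sized.

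**Working it through.** **Inputs from section B.** Planned effect 51 PRU; SD 54 (a within-patient change); two-sided alpha 0.05; power 0.80; 11 per group; statin effect 102 PRU; reference range 180-376 PRU off antiplatelet therapy. **Assumed, because the documents do not give them:** the share p not on a statin (10-50%), the statin gap D in this population, and SD 54 within statin groups for raw PRU.

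**1. The plan's own figure.** A paired t-test (noncentral t) with 51/54 = 0.944 needs n = 10.87, so 11, with power 80.6%. The stated 11 is reproduced.

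**2. The between-group test with no statin gap.** A two-sample t-test at 11 per arm with the same effect and SD has power 55.9%. It would need 19 per arm for 80%. This shortfall exists before statin status is considered.

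**3. Plausible size of the gap.**
- Upper end: 102 PRU, and 102/51 = 2.0 (the second study: 106/51 = 2.1).
- Closer population: the reference midpoint is (180 + 376)/2 = 278. Then 0.19 × 278 = 53 and 0.30 × 278 = 83 PRU, or 1.0 to 1.6 times 51. This carries percentages over from another assay and is only an illustration.

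**4. Power on raw day-28 PRU, unadjusted, 11 per arm.** Total SD = √(54² + p(1−p)D²). For D = 102 and p = 0.3: √(2916 + 0.21 × 10404) = 71.4.

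| Gap D (PRU) | p = 10% | 20% | 30% | 50% |
|---|---|---|---|---|
| 51 | 53% | 50% | 49% | 48% |
| 53 | 52% | 50% | 49% | 47% |
| 83 | 48% | 43% | 41% | 39% |
| 102 | 45% | 39% | 36% | 34% |

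**5. Power on change from run-in.** A constant gap is in both the run-in and the day-28 value and cancels. Power stays at 55.9% with or without stratification.

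**6. What adjustment recovers.** Simulation at 11 per arm (8,000 replicates, raw scale, p = 20% and 50%):

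| Gap D (PRU) | Unadjusted t-test | Adjusted for statin use | Balanced by statin use and adjusted |
|---|---|---|---|
| 102 | 39%, 32% | 53%, 53% | 55%, 55% |
| 0 | 55%, 56% | 53%, 54% | 56%, 55% |

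With no treatment effect, rejection rates were between 4.4% and 5.3% throughout.

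**7. Chance imbalance.** Suppose 7 of 24 patients are off statins (assumed), with 12 per arm and D = 102. The hypergeometric distribution gives:

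| Split | Probability | Shift in the arm difference |
|---|---|---|
| 5-2 | 30.2% | 102 × 3/12 = 25.5 PRU |
| 6-1 | 6.4% | 102 × 5/12 = 42.5 PRU |
| 7-0 | 0.5% | 102 × 7/12 = 59.5 PRU |

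A split of 5-2 or worse has probability 37.1%, in either direction. At D = 53 a 5-2 split shifts the difference by 13 PRU.

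**The case against.** The strongest reply is that the documents give no PRU gap between familial hypercholesterolemia patients on and off statins. The 102 PRU figure is a change within coronary patients on clopidogrel with high residual reactivity; in people off antiplatelet therapy it would span about half the reference range (102/196). This stands. A reader might infer that the plan's own figures make statin status a driver twice the planned effect. They show only that this is the upper end of a plausible range. The plan does, however, rely on the same figure to size this trial, so it cannot treat it as irrelevant here.

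Second, SD 54 belongs to a change score, and section B speaks of describing reductions. On change, the level problem disappears. This also stands, but the scale of the between-group test is never stated, so the plan does not secure that protection.

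Third, a reader might infer that imbalance could readily create or hide an effect as large as the one sought. Even with D = 102, only the 7-0 split exceeds 51 PRU, with probability 0.5%. Most of the 37% is 5-2 splits worth half the planned effect.

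Fourth, a statin main effect does not address a different response by statin status, a yes/no factor ignores ezetimibe, and stratifying about 24 patients may leave one small stratum. These limit the gain but do not remove it.

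Finally, the figures take PRU as primary, as section B does; section F names thrombin-peptide stimulated activation. The two sections must be reconciled.

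**Conclusion.** The point holds as a precision issue. The plan mixes statin-treated and statin-free patients, states no stratification, and compares arms by a covariate-free test on an unstated scale. Statin status may be prognostic at roughly one to two times the planned 51 PRU.

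If raw day-28 PRU is tested, power at 11 per arm falls from 56% to about 47-53% for a gap of 51-53 PRU, or 34-45% for a gap of 102. These figures rest on the assumed SD of 54 and on 10-50% of patients being off statins. If change is tested, a constant gap costs nothing, and only an unquantified difference in response remains.

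It would be wrong to conclude that the comparison is invalid. Randomisation keeps it unbiased on average, and type I error stays near 5%. What suffers is precision and the ease of reading a single small trial.

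**What to change.** In section B, replace the two-group t-test with a linear model (ANCOVA) of day-28 PRU on treatment, placebo run-in PRU (days 7 and 14) and statin use at entry (yes/no). Run-in PRU is already collected and deals with level differences from any source, including background ezetimibe. Naming the model also settles the outcome scale.

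In section C, have the independent biostatistician generate the table in two strata, on or not on a statin at entry, with small permuted blocks.

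The cost is one or two degrees of freedom, one more item for the pharmacy to check, and possibly incomplete blocks in the smaller stratum. If statin status turns out not to matter, adjusting for it without stratifying costs about two points of power in the simulation. No extra patients, visits or assays are needed.

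The change does not bring the between-group comparison to 80% power. In the simulation, stratification with adjustment for statin use gave about 55%. Any further gain from run-in PRU depends on a correlation that the plan does not give. The shortfall from sizing on a paired test needs its own correction.

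### The primary endpoint is called 30-day treatment, but on the schedule as written the placebo-controlled comparison comes about 14 days after evolocumab starts, and no sample falls near 30 days on drug

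*Combined protocol and SAP*

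**What the plan says.** Part B of Proposed studies (Power Calculation, primary measure) fixes the timing: "we have revised our experimental design to have a primary endpoint of 30-day treatment". The reason precedes it in the same sentence: "Based on reported literature indicating additional effects of statins on platelet function following 30-day vs shorter periods of treatment".

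Two tests carry that label.

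- Between groups: "Between-group thirty day evolocumab treatment will be tested by standard two-group t-test", specified as "two-sided, evolocumab vs vehicle control group run in parallel".
- Within group: "Within-group thirty day evolocumab treatment will be tested by one-group paired t-test", with the subject's own placebo period as comparator. No study day is named for either test.

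The planning effect also comes from 30 days of treatment, with a statin: "In CAD patients treated with clopidogrel, the addition of atorvastatin for 30 days resulted in an absolute mean difference of" 102 PRU (SD 54). Part B halves this to 51 PRU because statins may act partly through routes other than LDL lowering.

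Part C (Study Design) gives the schedule. All subjects start on placebo, with samples at days 7 and 14. They are then randomised, half staying on placebo and half starting evolocumab 140 mg every 14 days, with samples at days 21 and 28. After that everyone receives evolocumab, with samples at days 84 and 196. Sample collection may vary by 1 to 3 days. Incomplete data from dropouts are to be used only if they reach at least day 28. The schedule figure (Fig. 2) is not shown in the text available.

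**The concern.** The between-group test needs a control group still on placebo. On the written schedule that group ends when everyone switches after the day-28 sample, while the evolocumab arm started only after the day-14 sample. A comparison described as thirty-day treatment would then rest on about half that exposure and, with dosing every 14 days, on one injection if the day-28 sample precedes the next dose.

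This is more than loose labelling, because the plan itself argues that duration matters and selects 30 days on that ground. A positive result would be credited to the wrong exposure. A null result could be read as no effect at 30 days, which the comparison would not have tested. The planning effect was not reduced for shorter exposure either: the halving was for mechanism.

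**Working it through.** **The plan's own sample size.** Inputs from part B: mean difference 51 PRU, SD 54, two-sided alpha 0.05, power 0.80, one-group paired t-test. The standardised effect is 51/54 = 0.944. With the noncentral t distribution, power is 0.757 at n = 10 and 0.806 at n = 11, so the stated 11 per group reproduces. With 102 PRU the requirement is 5 subjects (power 0.878); the stated 6 gives 0.954. The arithmetic is not at issue here.

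**Days on evolocumab.** Inputs from part C: evolocumab starts after the day-14 sample in the evolocumab arm and after the day-28 sample in the placebo-first arm. The sampling window is up to 3 days, taken here in either direction.

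Days on drug = sample day − start day; range = (sample day ± 3) − start day.

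| Sample | Evolocumab arm | Placebo-first arm |
|---|---|---|
| Day 21 | 21 − 14 = 7 (4 to 10) | 0 |
| Day 28 | 28 − 14 = 14 (11 to 17) | 0 |
| Day 84 | 84 − 14 = 70 (67 to 73) | 84 − 28 = 56 (53 to 59) |
| Day 196 | 196 − 14 = 182 (179 to 185) | 196 − 28 = 168 (165 to 171) |

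**Between-group test.** Day 28 is the last sample with a parallel placebo group. The shortfall from 30 days is 30 − 14 = 16, with range 30 − 17 = 13 to 30 − 11 = 19.

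**Within-group test.** On this count no sample in either arm falls between 18 and 52 days on drug.

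**Alternative day counts.**

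- Days 84 and 196 counted from the start of evolocumab: the day-84 sample would be at about 84 days on drug. There is still nothing near 30.
- Days 21 and 28 counted from randomisation: day 28 would be 28 days on drug (25 to 31), and the mismatch would close.

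**Power.** The documents give no 14-day effect, so the consequence for power cannot be derived. Purely as an assumption, if the 14-day effect were 100%, 75% or 50% of 51 PRU (51, 38.25 or 25.5), paired power at n = 11 with SD 54 would be 0.81, 0.56 or 0.29. Nothing in the documents says which, if any, applies.

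**The case against.** The strongest objection is that the schedule figure is missing. If it shows the day count restarting at randomisation, there is a placebo-controlled sample at about 28 days on drug and the label is close enough. Two features of the text are compatible with that. Part B says the design was revised to reach 30 days, so part C could be the revised schedule. And dosing every 14 days in the randomised period fits two doses before a restarted day 28 more naturally than one dose before a running day 28.

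Neither is decisive: the dosing phrase may only describe the regimen. Days 7, 14, 21 and 28 are listed as one weekly sequence, and no sentence restarts the count. But no sentence states where counting begins either. So the objection does not remove the point; it makes the relabelling conditional on the day-count origin.

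Three stronger readings might be inferred, and the documents do not support them:

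- **That the trial is shown to lose power through the shorter exposure.** There is no evolocumab time course for platelet function in the documents. The 14-day effect could be as large as at 30 days.
- **That day 84 could pass as the thirty-day result.** At 56 to 84 days on drug, depending on arm and day count, that is strained. Day 28 is the only visit nominally near 30, and the 28-day minimum for dropout data points the same way, although it does not define the analysis day.
- **That exposure at day 28 could vary more widely than 11 to 17 days.** This needs a window on the dosing visit as well, and the text gives one only for sample collection.

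**Conclusion.** The point holds on the text. The plan states a 30-day primary endpoint and labels both tests accordingly, but on the natural reading of part C the randomised comparison is at 14 days on evolocumab (11 to 17), 13 to 19 days short. The within-group test has no sample near 30 days either. The planning effect of 51 PRU remains half of a 30-day statin effect, with no allowance for duration.

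The conclusion rests on one running day count from the start of the placebo run-in, first evolocumab at day 14, and a 3-day window in either direction on sampling only. It would fall if days 21 and 28 are counted from randomisation. What is shown is a mismatch between the stated endpoint and the schedule, which changes what the primary result estimates. Bias or a quantified loss of power is not shown.

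**What to change.** First check Fig. 2 for the origin of the day count and put it in the text. If, as the text reads, days run from the start of the placebo run-in:

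1. State that origin.
2. Name day 28 as the primary time point for both tests, with the day-14 placebo sample as baseline.
3. Describe the primary result as a 14-day evolocumab effect in both test descriptions and in the conclusions.
4. State that the power assumption borrows a 30-day statin effect.
5. Label days 84 and 196 as before-after results without a parallel placebo control.

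If Fig. 2 shows that the count restarts at randomisation, say so and still name day 28 and the baseline; the relabelling in step 3 is then not needed.

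This costs wording only, with no extra visits or drug. On the running count, the price is a narrower claim: 14 days, not 30.

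If a 30-day effect is truly required, an optional redesign is to keep the randomised placebo for one more 14-day cycle, sample at about day 42 to 44 before the switch (28 to 30 days on drug), and move the 28-day dropout rule to that visit. That adds one placebo cycle for the 11 or 12 control patients, one blood and urine visit for everyone, and a 14-day delay before the control arm receives evolocumab. It is not part of the low-cost fix.
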